### **Results presentation**

Secondary endpoints will be summarized using n, mean, confidence interval of mean, SD, median, minimum and maximum. And p-value for paired comparison will be displayed for all post-baseline visits.

#### **Normality checking**

Distribution assumptions used for the statistical analysis will be examined by obtaining a normal plot and Shapiro-Wilk Test.

Non-parametric analyses, Wilcoxon signed-rank test will be conducted if the normality assumption does not hold.

### **Supportive Statistical Analysis**

#### **Bayesian Method 1 Endpoint/Variable**

Change from baseline at Weeks 52 in Multiple Sclerosis Quality of Life (MSQOL)-54 Composite scores following treatment with HB-adMSCs or Placebo.

#### **Bayesian model specification**

Construct a linear model for each visit in order to model within-subject observation covariance structures by multivariate normal (MVN) distribution in the MCMC procedure.

For subject i on treatment j the model can be written as:

$$CHG_{ijk} = \beta_0 + \beta_1 \text{ treatment} + \beta_2 \text{ baseline} + \beta_3 \text{strataEDSS} + \beta_4 \text{strataAge} + \beta_5 \text{strataGender} + \varepsilon_{ij} \quad \varepsilon_{ij} \sim \text{Normal}(0, \sigma^2)$$

Where CHGij refers to change from baseline in subject i = 1, 2, ..., n indicator variable, which is intrinsically formed within PROC MCMC from the design matrix.

Initial values of the MCMC chains will be selected at random. Seed for random number generation will be specified as "seed = 12345" with three MCMC chains of 8000 total iterations each (with 4000 of these discarded as burn-in iterations). The simulation size and number of burn-in iterations can be updated during the convergence check.

The choice of prior distribution for level two variances will follow Gelman's recommendations from the literature. Models will use weakly informative priors to maximize the influence of the present data on posterior probabilities (PP). The non-informative priors for the model parameters  $\sim \text{Normal}(0, \sigma^2 = 10)$  and  $1/\sigma^2 \sim \text{Gamma}(0.001, \text{rate} = 0.001)$  will be used.

Models were evaluated via posterior probability guidelines in the literature, suggesting that PP = 75% to 90% indicates "moderate evidence," PP = 91% to 96% indicates "strong evidence," and PP  $\geq 97\%$  indicates "very strong to "extreme evidence."

Consistent with prior research, a PP  $\geq 75\%$  (equivalent to a Bayes factor = 0.33 or 3.00) that an effect exists will be taken as a minimum threshold of evidence in favor of the alternative hypothesis. This probability was chosen to emphasize the value in identifying a signal for the effects of treatment group, time, and their interaction.

The median, standard deviation, and 95% credible intervals (CrI) of the posterior distribution will be used to provide a point estimate and corresponding range of uncertainty for the magnitude of each predictor effect, including treatment group.

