7. Visually confirm temperature tape is in biohazard bag and is within range (2° - 8° C), document compliance.
8. Visually confirm syringe is closed with cap.
9. Remove syringe from bag and begin mixing syringe, gently rocking back and as well as rolling between hands, bringing the study treatment to room temp, and suspending them into a homogenous solution. No particulates should be visible.
10. Inject the contents into a 250cc bag of normal saline for injection
11. Properly label the infusion bag with the subject ID, D.O.B, preparation date, time and expiration and cover it with an amber bag.

Once, the study treatment has been mixed by the unblinded pharmacist following the above procedures, the infusion nurse or designated study staff will administer the study treatment as follows:

1. Confirm that the subject number and DOB placed on the amber bag label belong to the subject receiving the infusion.
2. Administer the infusion solution over a period of 1h (infusion rate 4-5ml/min).
3. Do not store or reuse any unused portion of the infusion solution. Any unused product or waste material should be disposed in a biohazard container.
4. Complete the source documents of the visit to accurately collect the start and end times of the infusion and add comments if necessary.
5. The study's subject will be monitored for a total of 2 hours from drug exposure to discharge.
 - During the Investigational product administration (1 hour) vital signs will be measured at minute 0, 15, 30, 45, and 60.
 - Post infusion, vital signs will be measured at minute 90 and 120.
6. Follow study procedures as described in the schedule of assessments of the visit.

Investigational Product Assignment (Randomization and Blinding)

A total of 24 eligible subjects will be randomized to either placebo (approx. 12) or active drug (approx. 12) (HB-adMSCs) in a 1:1 balanced design. The randomization will be applicable only to eligible subjects. If a subject is not eligible during the screening process for study participation, this subject shall not be randomized to any group.

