9-Hole Peg Test		X		X		X		X	X
Multiple Sclerosis Quality of Life Inventory 54		X		X		X		X	X
Patient Health Questionnaire 9 (PHQ-9)		X							X
Study Treatments Administration		X	X	X	X	X	X		
24 hours Telephone Encounter		X	X	X	X	X	X		
Video Documentation		X				X			X
AE and SAE assessments		X	X	X	X	X	X	X	X

¹ Collection of laboratory samples (CBC, CMP & Coagulation Panel)

Study Visits 1 to 9.

Visit 1 – Screening.

At the Screening Visit (Visit 1), study participants' information will be collected by study's delegated personnel for evaluation of trial eligibility. The following information is required to determine eligibility:

1. Signing Informed Consent Form (prior to any trial-related activities).
2. Collection of demographic information, such as age, race, ethnicity, date of birth, gender, and relevant medical and surgical history.
3. Collection of Medical History and concomitant medications, including relevant information about the past and present health of study participants.
4. Inclusion and Exclusion criteria evaluation.
5. Measurement of vital signs including respiratory rate, body temperature, blood pressure, pulse rate, oxygen saturation, and measurement of weight and height.
6. Collection of laboratory samples, including Comprehensive Metabolic Panel (CMP), Complete Blood Count (CBC), Coagulation Panel, and Urine pregnancy test if female of childbearing potential.
7. Physical examination by Principal Investigator, including clinical assessments such as Expanded Disability Status Scale (EDSS).

Within 28 days of the Visit 1 - Screening, the principal investigator must decide participant's eligibility. Once, the eligibility of the subject has been confirmed by the principal investigator, the randomization process will be conducted.

Visit 2 and 6 – Infusion 1 (Baseline) and Infusion 5

The following procedures are required during this visit:

1. Update medical history and concomitant medications if any change occurred since last visit.
2. Measure vital signs including respiratory rate, body temperature, blood pressure, pulse rate, oxygen saturation and measurement of weight.
3. Collect laboratory samples, including Comprehensive Metabolic Panel (CMP), Complete Blood Count (CBC), Coagulation Panel and Urine pregnancy test if female of childbearing potential.

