#### HB-adMSCs - Placebo

Pairwise t-test will be performed on the efficacy endpoints to test the difference between baseline and week 52 (EOS) as secondary analysis. Data for all the efficacy outcomes will be checked for normality (Shapiro-Wilk Test). When there is a larger deviation of data distribution from normality, appropriate non-parametric test will be used.

Additionally, RMA and ANCOVA in a Bayesian framework using a non-informative prior will be conducted to estimate the posterior distribution and to estimate the probability that the true treatment difference of change from baseline to Week 4, Week 8, Week 16, Week 24, Week 32, Week 42 and Week 52.

Study population analyses including analyses of subject disposition, demographic and baseline characteristics, medical history, prior and concomitant medications.

Disposition summary includes, subject screened, randomized and disposition at end of study – Week 52 along with reasons for withdrawals. Subjects in different analysis populations also will be presented.

The screen failure table includes total number of screened subjects and reasons. The percentage in the screen failure table will be calculated based on total number of screened subjects as denominator.

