### 5.2.1. Definition of endpoint(s)

Objectives	Endpoints
Primary Objective	Primary Endpoint

To investigate the efficacy of intravenous infusions of HB-adMSCs vs Placebo in patients with Multiple Sclerosis as determined by improvements in Multiple Sclerosis Quality of Life (MSQOL)-54 Instrument. (Time frame: Baseline to Week 52).

	

Changes from Baseline at Weeks 52 in Multiple Sclerosis Quality of Life (MSQOL)-54 Instrument scores following treatment with HB-adMSCs or Placebo.

 
This 54-item questionnaire provides 12 subscales, two summary scores, and two extra single-item measures. The subscales are physical function, role limits-physical, emotional role restrictions, pain, emotional well-being, energy, health perceptions, social function, cognitive function, health distress, overall quality of life, and sexual function.

Data from the MSQOL-54 will be scored according to the scoring algorithm suggested by the authors of the questionnaires ([Vickrey](#) 1995). Scale scores will be generated by averaging the items within scales and transforming the mean scores linearly from 0 to 100 possible scores, with higher scores indicating a better QOL. Physical and mental health composite scores will be generated by weighting the sum of selected scales to generate a simplified two-factor solution and the composite scores of the MSQOL-54.

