

• To compare the HB-adMSCs to Placebo on Change from baseline, a Repeated measures analysis (RMA) model will be fitted

• Terms fitted in the mixed effect model will include:

• All primary endpoint efficacy measurements available at post-baseline at scheduled measurements will be response variable in a linear mixed model using an unstructured residual covariance matrix.

• The model will include:

• Fixed factors: treatment and visit

• Fixed stratification factors: Multiple's sclerosis severity (Mild disability (EDSS < 4) ; Moderate disability (EDSS > 4 and < 6.5)), Age (< 55 ; > 55) and Gender (Female ; Male)

• Covariate: baseline

- Furthermore, the model will include:
  - Interaction terms between treatment and visit

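### The supportive Bayesian models call a Normal(0, variance 10) prior non-informative on 0-100 composites, and the Method 2 equation contradicts its own text on covariance and per-visit effects

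*SAP*

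**What the plan says.** SAP 5.1.1 announces "RMA and ANCOVA in a Bayesian framework using a non-informative prior will be conducted to estimate the posterior distribution", and wants a probability statement about "the true treatment difference of change from baseline to Week 4, Week 8, Week 16, Week 24, Week 32, Week 42 and Week 52".

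SAP 5.2.2, Supportive Statistical Analysis, specifies two models. In both, one sentence calls the priors weakly informative and says they are meant to let the data dominate. The next begins "The non-informative priors for the model parameters" and gives Normal(0, variance 10), plus a Gamma(0.001, 0.001) prior on a single precision. The SAP gives no reason for the value 10 and plans no prior-sensitivity analysis. It does not centre baseline in either equation and does not state how treatment is coded.

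The outcome is change in composites built from subscales scored by "transforming the mean scores linearly from 0 to 100 possible scores" (SAP 5.2.1).

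For Method 2, the text says within-subject covariance will be modelled by a multivariate normal distribution. The equation beneath it has terms for treatment, baseline, visit and the three strata, and a scalar error with variance sigma-squared. It has no covariance matrix, subject effect or treatment-by-visit term. The frequentist counterpart in the same section is a "linear mixed model using an unstructured residual covariance matrix" and adds "Interaction terms between treatment and visit".

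**The concern.** The SAP grades PP into moderate (75% to 90%), strong (91% to 96%) and very strong (97% and above) bands. A reader told that the prior is non-informative will take the band as a statement about the data. If the prior outweighs the data, the band and the estimate largely reflect an undeclared assumption that effects beyond about 6 points are implausible. The planned convergence checks would not reveal this, because a chain can converge perfectly well to a prior-dominated posterior.

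The Method 2 mismatch means two competent programmers could fit two different models. One gives a treatment difference at each visit and respects the correlation between a patient's visits. The other gives a single difference and counts repeated visits as independent patients.

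**Working it through.** **The plan's own figure.** The SAP equates PP 75% with a Bayes factor of 3.00 or 0.33. At prior odds of 1, 0.75/0.25 = 3.00 and the inverse is 0.33, so it reproduces. The plan gives no SD, correlation, intercept, slope or power calculation.

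**Inputs.** Prior variance 10 (SAP 5.2.2). About 12 per arm (Protocol, Investigational Product Assignment). Composite weights sum to 1.00 for both composites (SAP, Derivation of MSQOL-54 Composite Scores), so each runs from 0 to 100. The row for the "Multiple Sclerosis Quality of Life Inventory 54" in Protocol Table 4 marks four post-baseline visits: Weeks 8, 24, 42 and 52. Assumed: residual SD 8 to 20, between-visit correlation 0.5 to 0.7.

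**Prior scale.** sqrt(10) = 3.16, and 1.96 × 3.16 = 6.2 points.

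**Method 1, closed form.** SE² = SD² × 2/12. The data receive weight w = 10/(10 + SE²), so shrinkage is 1 − w. A z = 1.96 result has PP = Φ(1.96 × √w). The z needed for PP 97% is 1.881/√w.

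| SD | SE² | Shrinkage | PP at z = 1.96 (flat prior: 0.975) | z for PP 97% (flat prior: 1.88) |
|---|---|---|---|---|
| 8 | 10.67 | 52% | 0.91 | 2.70 |
| 10 | 16.67 | 62.5% | 0.885 | 3.07 |
| 12 | 24.0 | 71% | 0.86 | 3.47 |
| 15 | 37.5 | 79% | 0.82 | 4.10 |
| 20 | 66.67 | 87% | 0.76 | 5.21 |

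**Intercept and coding.** The same prior covers the intercept. If the true intercept is far from zero, part of the misfit moves into whichever arm is coded 1. The full Method 1 equation was fitted to simulated null data (assumed intercept 22, slope −0.4, uncentred baseline with mean 55 and SD 15, residual SD 8). The mean estimated benefit was about +0.8 to +0.9 with active coded 1 and about −0.9 with placebo coded 1. With baseline centred it was about 0.

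**Method 2 programmed literally.** With four visits, the model takes the variance of the treatment estimate as SE²/4. The true variance is (SE²/4)(1 + 3ρ). With w₄ = 10/(10 + SE²/4), the null rate of PP ≥ 97% for benefit is 1 − Φ(1.881/√(w₄(1 + 3ρ))).

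- SD 15, ρ 0.5: SE²/4 = 9.375, w₄ = 0.516, 1.881/√(0.516 × 2.5) = 1.656, giving 4.9%.
- SD 10, ρ 0.7: SE²/4 = 4.167, w₄ = 0.706, 1.881/√(0.706 × 3.1) = 1.272, giving 10.2%.
- SD 20, ρ 0.5: SE²/4 = 16.67, w₄ = 0.375, 1.881/√(0.375 × 2.5) = 1.943, giving 2.6%, so no excess.

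Full fits with either a centred baseline or zero intercept and slope gave 4.3% to 10.5% over SD 10 to 15 and correlation 0.5 to 0.7. The nominal rate is 3%.

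**Widening the prior alone.** With w₄ near 1, the rate is 1 − Φ(1.881/√2.5) = 11.7% at ρ 0.5 and 1 − Φ(1.881/√3.1) = 14.3% at ρ 0.7. Full fits gave 11% to 17%. A wider prior therefore does not repair the literal equation. It removes the shrinkage that was partly masking the overstated precision.

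**The case against.** **These analyses are only supportive.** True; the SAP labels them so. A reader might infer that the trial's main conclusion is at risk. It is not: the primary ANCOVA and the frequentist repeated measures model use neither the prior nor this equation.

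**The equation is shorthand for the marginal distribution.** This is possible, and then the excess null rate does not arise. But the SAP states a prior for one variance only and none for a covariance matrix, so the multivariate model is still not fully specified.

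**Shrinkage is conservative.** A sceptical prior is a legitimate choice if it is declared and justified. Here it is labelled the opposite.

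**A tempting stronger reading** is that the prior pushes a null effect towards benefit, or that Method 2 inflates the top band in general. The documents do not support either. The SAP does not state the treatment coding, and reversing it reverses the shift. In the non-zero-intercept, uncentred set-up, literal Method 2 gave null PP ≥ 97% of about 15% with active coded 1 and about 4% with placebo coded 1.

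**The interaction sentence proves little.** The Method 2 remark about treatment, time and their interaction appears word for word under Method 1, a single-visit model, as does the multivariate normal sentence. Better evidence of intent is the per-week difference in SAP 5.1.1, Method 2's own by-week endpoint, and the matching repeated measures model.

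**PP direction.** The SAP speaks of PP for the existence of an effect, and its hypotheses are two-sided. The null rates here count benefit only, and any-direction rates would differ.

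**Conclusion.** Both parts hold. The prior is mislabelled: at every SD tried it outweighs the data, shrinking the estimate by 52% to 87% at SD 8 to 20 with 12 per arm. The size depends on the assumed SD. With uncentred baseline the estimate can also shift either way, depending on coding.

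The Method 2 text and equation conflict, and the SAP does not say which governs. Taken literally, the equation cannot deliver per-visit differences. It also raises the null rate of PP ≥ 97% for benefit from 3% to about 4% to 10.5% at SD 10 to 15 and correlation 0.5 to 0.7, absent intercept misfit. There is no excess at SD 20 with correlation 0.5. The two faults act in opposite directions on PP, so both need correcting.

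The reuse of beta-3 for visit and EDSS stratum, and an index of 1 to 6 for seven listed weeks, are minor slips in the same lines. The point should be settled before unblinding but does not threaten the primary analysis.

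**What to change.** **Prior.** Centre baseline and state the treatment coding. Then either use a diffuse prior scaled to the endpoint (for example variance 10^4 on the 0-100 scale), or declare the prior informative, justify its scale and add a prior-sensitivity analysis. Use one label in SAP 5.1.1 and in both Bayesian methods.

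**Method 2.** Rewrite the equation with:

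- a multivariate normal, unstructured residual over the collected visits (Weeks 8, 24, 42 and 52);
- a stated weak prior for that covariance matrix, for example inverse-Wishart with minimal degrees of freedom, with a sensitivity check because n is only 24;
- treatment-by-visit terms;
- separate coefficients for visit and EDSS stratum, and a correct visit index.

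**Reporting.** State the direction in which PP is computed.

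The cost is SAP wording, modest extra programming and wider credible intervals. It needs no new data and places no burden on patients.

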### 3. STATISTICAL HYPOTHESES

The primary analysis will test whether HB-adMSCs is superior to Placebo according to the following statistical hypotheses:

**Null hypothesis H0:** The difference in change from baseline at Weeks 52 in Multiple Sclerosis Quality of Life (MSQOL)-54 Instrument scores between treatment groups (HB-adMSCs – Placebo) is equal to zero.

**Alternative hypothesis H1:** The difference in change from baseline at Weeks 52 in Multiple Sclerosis Quality of Life (MSQOL)-54 Instrument scores between treatment groups (HB-adMSCs – Placebo) is not equal to zero.

Secondary analysis will be tested for mean difference for change from Baseline to Week 52 for efficacy endpoints for both treatment groups,

**Null hypothesis H0:**  $\Delta = 0$

**Alternative hypothesis H1:**  $\Delta \neq 0$

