#### 5.1.1. General Methodology

Unless otherwise stated, all hypotheses will be tested at a 2-sided significance level of 0.05 and 95% confidence interval. All continuous measurements will be summarised descriptively at each visit by treatment using observed data.

Summary of continuous variables will be presented using N, Mean, 95% confidence interval of mean, Standard Error of mean (SE), Standard Deviation (SD), Median and Range (Minimum and Maximum). The categorical variables will be presented using number and percentage based on N.

For measurements over time mean values will be plotted to explore the trajectory over time. Observed data will be used as the basis for plotting data along with bars as +/- SE, not otherwise specified.

As a primary analysis, a standard Analysis of Covariance (ANCOVA) will be applied for primary and secondary endpoint to test the significance of the effects of the treatment at Week 52. The model includes treatment as fixed factor and the corresponding baseline value as a covariate.

A parametric Repeated Measures Analysis (RMA) Model will be applied as a secondary analysis to test the significance of the effects of the treatment at Week 4, Week 8, Week 16, Week 24, Week 32, Week 42 and Week 52 including baseline as covariate.

Presentation of results from a statistical analysis model will include the estimated mean treatment effects (Least Square Means (LSMeans)). For all endpoints analysed statistically, estimated mean treatment differences will be presented together with two-sided 95% confidence intervals and p-values,

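### The supportive Bayesian rule treats a posterior probability of 75% as a Bayes factor of 3 for the alternative; in the planned model it can only be directional odds, and its strength depends on the prior and the noise

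*SAP*

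**What the plan says.** SAP section 3 sets a point null. The between-group difference in week 52 change on MSQOL-54 is zero under H0, and under H1 it "is not equal to zero". SAP 5.1.1 adds that "all hypotheses will be tested at a 2-sided significance level of 0.05", and that "RMA and ANCOVA in a Bayesian framework using a non-informative prior will be conducted to estimate the posterior distribution". The rest of that last sentence, which should say which event the probability refers to, names neither a direction nor a margin.

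SAP 5.2.2 then gives two Bayesian models under a supportive heading: Method 1 for week 52 and Method 2 for all visits. Each is a linear regression. The text introducing "The non-informative priors for the model parameters" gives a Normal distribution with mean 0 and variance 10, and the sentence before it calls the priors weakly informative. Both methods carry the same rule: PP of at least 75% that an effect exists is called "equivalent to a Bayes factor = 0.33 or 3.00" and "will be taken as a minimum threshold of evidence in favor of the alternative hypothesis". Both also label bands of PP: 75% to 90% moderate, 91% to 96% strong, and 97% or more very strong to extreme. The stated purpose of the 75% level is to help identify a signal. 95% credible intervals are already planned.

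**The concern.** A Bayes factor for H1 against H0 compares how well a non-zero difference and a zero difference predict the data. The planned model puts no prior probability on exactly zero, so within it the probability that the difference is non-zero is 1 whatever the data show. What can be computed is the probability that the difference lies above zero, or above some margin. Turning 75% into odds of 3 then compares benefit with harm and says nothing about no effect.

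What is at stake is the wording of the report. The trial has about 12 subjects per arm and SAP section 6 gives no power justification, so a non-significant primary ANCOVA is a realistic outcome. The SAP would then allow a weak directional lean to be reported as moderate evidence for the alternative with a Bayes factor of 3.

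**Working it through.** **Inputs from the documents.** PP threshold 75% and Bayes factor 3.00 or 0.33 (SAP 5.2.2); H0 difference = 0, H1 difference not 0 (SAP 3); two-sided 0.05 and a non-informative prior (SAP 5.1.1); written prior Normal(0, variance 10) (SAP 5.2.2); two composites, built from subscales scored 0 to 100 (SAP 5.2.1); about 12 per arm (protocol, Investigational Product Assignment).

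**Assumed.** The documents give no standard deviation. I take a standard error (SE) of the treatment difference of 4, 6 or 8 points. With SE = SD × √(2/12), this is a residual SD of about 10, 15 or 20 points. I use a normal likelihood with known SE and apply the prior to the treatment coefficient only.

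**Step 1: the plan's own figure.** 0.75/0.25 = 3.00 and 0.25/0.75 = 0.33. The figure reproduces as posterior odds with 1:1 prior odds. In this model the two sides are difference > 0 and difference < 0.

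**Step 2: non-informative prior.** PP = Φ(z), where z is the estimate divided by its SE, so PP = 75% gives z = 0.674.
- Two-sided p = 2 × (1 − 0.75) = 0.50.
- The largest Bayes factor against zero, over all priors on the effect, is exp(z²/2) = exp(0.674²/2) = 1.26. A factor of 3 needs z of at least √(2 ln 3) = 1.48, which is a PP of at least 93%.
- With no effect, PP ≥ 75% for benefit occurs in 25% of trials per composite, and in 50% counting either direction. For benefit on at least one of the two composites it occurs in 33% (assumed correlation 0.8) to 39% (correlation 0.4).
- The very-strong band starts at PP = 97%, which is p = 0.06 and so just misses the SAP's own 0.05 level.

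**Step 3: prior as written.** Let w = 10/(10 + SE²). PP = 75% now needs z = 0.674/√w. The null rate per direction is 1 − Φ(z), p is twice that, and the Bayes factor against zero under this prior is √(1 − w) × exp(w z²/2) = 1.26 × √(1 − w).

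| Assumed SE | w | z at PP = 75% | Two-sided p | Null rate per direction | Bayes factor against zero |
|---|---|---|---|---|---|
| 4 | 0.385 | 1.09 | 0.28 | 13.8% | 0.98 |
| 6 | 0.217 | 1.45 | 0.15 | 7.4% | 1.11 |
| 8 | 0.135 | 1.83 | 0.07 | 3.3% | 1.17 |

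The same 75% therefore stands for p = 0.50 or p = 0.07, depending on the prior used and the noise in the data. In none of these cases is the Bayes factor near 3.

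**Step 4: would 97.5% be a safe replacement?** Under a flat prior, PP = 97.5% is p = 2 × 0.025 = 0.05. Under the written prior it needs z = 1.96/√w = 3.16, 4.20 or 5.33 for SE 4, 6 or 8, that is, an observed difference (z × SE) of about 13, 25 or 43 points. The null rate per direction is then 0.08% or less. The match to the 5% level holds only with a diffuse prior.

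**The case against.** The strongest reply is that this analysis is supportive, that inference rests on the two-sided 0.05 ANCOVA, and that 75% is presented as a minimum level for finding a signal. That stands, and it limits the consequence. It does not make a directional probability into a Bayes factor against no effect, and a signal-finding purpose justifies a descriptive probability rather than a claim for H1.

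A second reply is that the operative prior is the written one, so p = 0.50 and the 1.26 ceiling do not describe the model that will be run. This also stands. A reader might infer that PP = 75% always means p = 0.50, or that the 1.26 ceiling alone rules out a factor of 3. The documents do not support that: with the written prior, exp(z²/2) at PP = 75% is 1.81, 2.85 or 5.38 for SE 4, 6 or 8, so the ceiling can exceed 3. The conclusion rests instead on the Bayes factor actually obtained under that prior, about 1.0 to 1.2.

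Third, a Bayes factor of 3 would be correct in a model giving prior probability one half to exactly zero and one half to a non-zero effect. That is true, but the SAP specifies no such model.

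Finally, the rule names no direction. A reader might infer that every chance hit would be credited to HB-adMSCs; by symmetry, half of the either-direction hits under the null would favour placebo.

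**Conclusion.** The equivalence and the claim of evidence for the alternative are wrong as written, in both Bayesian methods. The event behind PP is undefined, and in this model the ratio of 3 can only be directional odds.

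The size is conditional. Under a non-informative prior, the threshold is p = 0.50 with a 25% null rate for benefit per composite. Under the written prior it is p of about 0.28 to 0.07 with a null rate of about 14% to 3% per direction, resting on the assumed SE of 4 to 8 points. The label has no fixed meaning across these cases, and the SAP's two names for its prior leave unclear which case is intended.

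A reader might infer that the trial's type I error is inflated. It is not: the primary ANCOVA is separate from this rule. The harm is overstated supportive evidence, and the correction should be made before the analysis.

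**What to change.** In SAP 5.2.2, for both Bayesian methods:
- Delete the Bayes-factor equivalence and the statement that PP ≥ 75% is evidence for the alternative. The evidence bands should go too, or be described as directional only.
- Define PP as P(difference > 0 | data), or as the probability of exceeding a stated margin, and complete the unfinished sentence in SAP 5.1.1 to match.
- Report PP as descriptive, beside the credible interval already planned.
- Reconcile the non-informative and weakly informative labels with the variance of 10. If non-informative is meant, use a genuinely diffuse prior on the treatment effect.
- For any threshold kept, state its null hit rate under the prior actually used. Describe 97.5% as matching the two-sided 5% level only if that prior is diffuse.

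If a Bayes factor against no effect is wanted, a model with prior mass at zero has to be specified. Otherwise the cost is SAP wording, possibly one prior setting, and a short calculation of hit rates. The downside is that fewer supportive results can be labelled as evidence.
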